7.2. Interim Analyses

Administrative interim analyses on safety and efficacy or on PK, and selected biomarkers may be provided at several times prior to completion of the study in order to facilitate program decisions and to support study presentations or publications. No formal interim analyses are planned for this study.

7.3. Multi-Center Studies

This is a multi-center study. Given the small sample size of the study, no site effect will be considered in any statistical analysis.

7.4. Multiple Comparisons / Multiplicity

No adjustments for multiple tests or multiple comparisons will be utilized.

7.5. Examination of Subgroups

Analysis endpoints of safety and efficacy variables may be further explored with the following subgroups:

- Tumor ratio (1:4, 1:3, 1:2 or dose set by longest diameter formulas)
- Dose schedule (every 2 weeks versus every 4 weeks)
- Superficial tumor injection subjects versus deep tumor injection subjects
- Tumor type (Sarcoma)
- Status of prior treatment with platinum-based antineoplastics or vinca alkaloid therapies
- Subjects with less than 2 tumors injected compared to those with ≥ 2 tumors
- Tumor burden: subjects receiving $\geq 40\%$ of tumor burden injected versus those receiving $< 40\%$; tumor burden is calculated based on EDC documentation of target, bystander, non-target, and new tumors. Subjects receiving $\geq 40\%$ of baseline total tumor burden injected overall (during the course of therapy) and at first dose will be explored. For overall, the sum of all injection volumes will be used in the calculation.

The subgroups to be analyzed for each endpoint are described in Section 8, Section 9, and Section 10.

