There are 4 cohorts that use a maximum total fixed dose of INT230-6 of 175 mL for all 5 induction doses and along with maintenance doses. The maintenance dose is an INT230-6 dose given every 9 weeks +/- 10 days up to a maximum total dose amount of 175 mL. The fixed dose cohorts are EC3, DEC2, FEC and potentially GEC and each follows the Q2 week INT230-6 dosing schedule at drug load to tumor volume ratio of 1:3 into both superficial and deep tumors for tumor types defined in the appropriate supplement.

Cohort 7 (EC3) explores administration of INT230-6 monotherapy for any tumor type.

Cohort 8 (DEC2) combines a fixed dose of pembrolizumab with the same INT230-6 dosing regimen of EC3 as outlined in Supplement A.

Cohort 9 (FEC) combines a fixed dose of ipilimumab with the same INT230-6 dosing regimen of EC3 as outlined in Supplement A.

Future Cohort 10 (G cohort) combines INT230-6 with other molecules.

Additional cohorts can be added depending on review of safety data by the Study Steering Committee. All cohorts and decisions to escalate the dose and introduce new subject populations will be governed by the Study Steering Committee (SSC).

Expansion cohorts

The SSC reviewed the safety and any available biologic and/or tumor measurement data, a decision to open expansion cohorts of 10-16 subjects with a single tumor type was made. These groups will allow for better point estimates of the safety and preliminary efficacy in a homogenous population.

Number of subjects (planned):

The sample size (estimated to be between 100 and 175 subjects) during dose escalation cannot be precisely determined but depends on the observed toxicity. In expansion cohorts, up to 16 subjects will be treated at fixed doses in a tumor type, to provide preliminary assessment of tumor response, in addition to safety assessment.

Diagnosis and main criteria for inclusion:

Key Inclusion Criteria

1. The participant (or legally acceptable representative if applicable) provides written informed consent for the trial.
2. Men and Women ≥ 18 years of age on the day of signing consent.
3. Have an Eastern Cooperative Oncology Group (ECOG) performance status ≤ 2 ; (**for pembrolizumab and ipilimumab combinations please see supplements DEC/DEC2 and FEC for ECOG criteria**).
4. Populations: INT230-6 will be injected into deep or superficial tumors for subjects with histologically or cytologically confirmed advanced or metastatic cancers; (**for pembrolizumab**

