The Study Steering Committee is comprised of the majority of study investigators plus representatives from the Sponsor. The SSC will review safety data regularly in an ongoing basis on all subjects. Decisions to increase the number of subjects in a cohort, to increase the loading concentration injected into the tumors, and the decision to begin treating deep tumors will require agreement from this committee. The SSC will review the data on any sentinel subjects and facilitate the decision to recruit more subjects.

Expansion Groups

The SSC has reviewed the safety and any available biologic and/or tumor measurement data from phase 1, and recommended opening expansion groups of 10-16 subjects with single tumor types. These groups allow for better point estimates of the safety and preliminary efficacy in a homogenous population of subjects. These groups try to optimize drug exposure (i.e., maximum injection volume and drug load) to facilitate the optimal tumor destruction potential.

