14.2.5. Exploratory Biomarker (Immune Function and others) Data Set

All subjects who receive at least one dose of INT230-6 and have at least one measurement for a specific marker will be included in the data set for that marker. All treated subjects with at least one baseline measurement will be included in predictive analyses; treated subjects with baseline measurement and at least one on treatment measurement will be included in pharmacodynamic assessments. Blood biomarker sampling has been eliminated in Amendment 6.

14.2.6. **Retreatment Population**

For cohorts A1, B1, EA, EC, EC2, DEC, those subjects who have completed treatment and have not started any subsequent anti-cancer therapy were eligible for retreatment. Subjects who qualified for re-initiation of treatment were evaluated for safety and efficacy based on availability of data.

14.3. **Statistical Considerations**

Please refer to the Statistical Analysis Plan (SAP).

14.3.1. **Demographics and Baseline Characteristics**

Subject demographics and baseline characteristics including age, sex, race, ethnicity, weight, baseline disease diagnosis, and medical conditions will be summarized by dose level using descriptive statistics.

14.3.2. **Extent of Exposure**

The dose of INT230-6 taken by subjects will be summarized by total dose and number of tumors injected. Additional parameters will be summarized, such a reason for study drug interruption and number of tumors with drug exuded. A by-subject listing of treatment exposure will be generated.

Combination study drugs for cohorts 7 and higher will also be summarized. Details will be provided in the statistical analysis plan.

14.3.3. **Tumor Response.**

The primary efficacy endpoint of disease control rate (DCR), defined as the sum of complete, partial and stable disease responses divided by the total number of subjects in the efficacy population, will be determined per iRECIST criteria for fixed dose and expansion cohorts. DCR will be tabulated by overall and by tumor type. Exploratory analysis will be conducted by cohort, Phase 1 cohorts (monotherapy and PD-1), Phase 2 cohorts (monotherapy, PD-1 and CTLA-4), Phase 1 and 2 cohorts (monotherapy and PD-1), tumor types, study visit, number of INT230-6 doses, number of cycles of INT230-6 (i.e., retreatment), and number of prior lines of therapy. Since iRECIST methods were not implemented at the time of dose escalation, DCR for these cohorts will be analyzed per RECIST v1.1.

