4.1.2. Highest Dose

Monotherapy Cohort EC3 and Combination Cohorts DEC2 and FEC shall use up to a maximum dose of INT230-6 of 175 mL with the number of tumors being dosed per session to be decided by the investigators. The dose being set by the subject's tumor burden. After completing 5 doses of INT230-6, a maintenance single treatment of INT230-6 by intratumoral injection of up to 175 mL should be given every 9 weeks \pm 10 days into target tumors until either progressive disease, radiologic or biopsy confirmed complete response, or two years. Refer to the Study Protocol for details on combination drug dosing. Decisions to increase the number of subjects in a cohort, to change the INT230-6 dose into the tumors, and the decision as to which populations to include will require consensus from the SCC.

Up to a maximum of 44 subjects will be enrolled in Cohort DEC2. Review of DLTs will continue for Cohort DEC2 with the following conventions:

- If 2 subjects experienced a DLT, an additional 6 subjects will be entered and followed for a 28 day DLT window
- If > 3 subjects experience a DLT, the safety data will be reviewed by the SSC to determine if a lower dose or lower loading ratio per tumor of INT230-6 could be explored

- If the DLT rate is excessive during enrollment of the additional 44 subjects, the SSC reviewed the data and determine how the INT230-6 dose will be decreased, and the number of additional patients enrolled on the study at the lower dose

For Cohort FEC, up to 15 subjects could be recruited into each of the following cancer types: metastatic hepatocellular carcinoma (HCC), breast cancer (BC) and soft tissue sarcoma. The overall cohort will employ a 6 subject safety lead-in to evaluate safety and toxicities. The safety data will be reviewed by the SCC to determine whether expansion to the total of 45 subjects should be permitted. For the HCC subjects in Cohort FEC, the first accrued HCC subject shall be evaluated at Day 28. This sentinel HCC subject must receive two INT230-6 doses and 1 ipilimumab dose prior to accruing the remainder of the HCC portion of the cohort. If there are more than 2 DLTs in the HCC cohort, the SSC will evaluate de-escalation of ipilimumab.

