5. SAMPLE SIZE DETERMINATION

The sample size was estimated to be between 100 and 175 subjects during dose escalation and expansion. The final enrollment consisted of 110 subjects two of whom participated in more than one cohort. Expansion cohorts may treat subjects in a specific tumor type (e.g., sarcoma that would include chordoma) to provide additional safety information and preliminary assessment of tumor response within a disease indication.

With 16 subjects treated in an expansion cohort in a given tumor type, the 90% confidence interval for an objective response rate would be 5.3% to 42% if 3 (19%) subjects had a response, 9.0% to 48% if 4 (25%) subjects had a response and 13.2% to 54.8% if 5 (31%) subjects had a response.

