9. EFFICACY ANALYSES

Due to the method of action of the INT230-6 therapy observed over the course of the study, proper assessment utilizing RECIST or iRECIST was not possible. A response across all lesions using sum of diameters to assess efficacy over time using response criteria was not utilized. Thus, efficacy analyses will largely focus on the response of individual tumors (injected and bystander) as opposed to an overall tumor response, and any overall response will utilize the modified response criteria defined below.

Efficacy analyses will be conducted on the All Treated Population (ATP), the Response Evaluable Population (REP), and the Scan Evaluable Population (SEP). RECIST 1.1 assessments were not collected. Rather injected tumor response and non-injected tumor response utilizing some of the RECIST criteria were evaluated. Sponsor utilized RECIST principles with the injected and non-injected tumor measurements obtained. Efficacy will be determined based on a modified version of RECIST 1.1 criteria. Specifically, complete response (CR) and partial response (PR) will be defined for injected tumors followed per RECIST 1.1 utilizing target lesions. Progressive disease will be determined by clinical or radiological deterioration leading to the subject being taken off-treatment at the discretion of the investigator. Stable disease (SD) is defined as any adequate assessment not considered CR, PR, or progression. The appearance of a new lesion will not necessarily be considered progression and if possible will be assessed. Any post-baseline visit where a target lesion present at baseline was not assessed will result in a Not Evaluable (NE) assessment for that lesion. Data will be presented by treatment and, when indicated, by subgroups.

The primary efficacy parameter is the disease control rate (DCR), defined as the number of subjects obtaining a best overall response of either CR, PR, or SD as described above divided by the total number of subjects in the analysis population. The DCR will be presented with accompanying 95% exact binomial confidence intervals for each study part for the ATP population, REP, SEP, and by subgroup.

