10.3. Vital Signs

Vital sign measurements and change from baseline will be summarized by cohort, tumor type and study visit using descriptive statistics. Vital signs include weight, systolic blood pressure (SBP), diastolic blood pressure (DBP), body mass index (BMI, derived), heart rate, oxygen saturation, and temperature. Individual vital sign measurements will be listed.

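### The protocol plans DCR by tumor type and sizes its expansion groups that way, but the SAP text commits to no tumor-type DCR beyond an optional sarcoma subgroup and declares no change

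*SAP*

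**What the plan says.** **Protocol.** Section 14.3.3 states: "DCR will be tabulated by overall and by tumor type". The synopsis, under efficacy analyses, says the same, and neither place limits the tabulation to one cancer. Under Expansion Groups in Section 5.2, the steering committee "recommended opening expansion groups of 10-16 subjects with single tumor types". The synopsis gives the reason: "These groups will allow for better point estimates of the safety and preliminary efficacy in a homogenous population". Section 14.1 states precision for 16 subjects at one dose and in one tumor type.

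**SAP.** The same design unit is kept. Section 5 opens its precision statement with "With 16 subjects treated in an expansion cohort in a given tumor type". For cohort FEC, Section 4.1.2 says that "up to 15 subjects could be recruited into each of the following cancer types", and names hepatocellular carcinoma, breast cancer and soft tissue sarcoma. Table 2 makes DCR the primary endpoint of DEC2 and FEC.

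For the analysis, Section 9 says: "The DCR will be presented with accompanying 95% exact binomial confidence intervals for each study part", in three populations and by subgroup. Section 7.5 lists subgroups that may be explored; its tumor-type line is "Tumor type (Sarcoma". Section 7.1 pools DEC with DEC2 and treats FEC as one group. Section 13 reports no changes.

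**The concern.** A team that follows the SAP text would produce DCR for the pembrolizumab group and the ipilimumab group, possibly with a sarcoma row. It would have no instruction to produce DCR for the other cancers in which expansion groups were opened.

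A rate pooled over different cancers depends on how many subjects of each type were recruited. It does not supply the homogeneous-population estimate that justified those groups. The departure from the protocol is also undeclared, so a reader of the study report would not learn that a planned tabulation had been dropped, or why sarcoma alone was kept.

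**Working it through.** **1. Passages side by side.**

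| Item | Protocol | SAP |
|---|---|---|
| Unit for sizing | 10-16 subjects per tumor type (5.2, 14.1) | 10-16, single tumor types (4.1.3); 16 in a given type (5); FEC cap of 15 per type (4.1.2) |
| DCR tabulation | Overall and by tumor type (14.3.3, synopsis) | Study part, population, subgroup (9); subgroups of interest (synopsis) |
| Tumor types named for subgroups | No restriction | Sarcoma only, optional (7.5) |
| Declared change | – | None (13) |

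SAP 7.5 refers to Sections 8 to 10 for the subgroups that apply to each endpoint. Section 9 names no tumor type for DCR, and the only tumor-type survival curves in 9.2 are for sarcoma. The variable is available: prior therapy is summarized by tumor type (8.3), and for vital signs Section 10.3 says "Vital sign measurements and change from baseline will be summarized by cohort, tumor type and study visit".

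**2. The plan's own precision figure.** The exact (Clopper-Pearson) interval at level 1 − α for x of n has lower limit Beta⁻¹(α/2; x, n − x + 1) and upper limit Beta⁻¹(1 − α/2; x + 1, n − x). With n = 16:

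| x/16 | Stated 90% (SAP 5) | Recomputed 90% | Exact 95%, the level planned for DCR |
|---|---|---|---|
| 3 | 5.3% to 42% | 5.3% to 41.7% | 4.0% to 45.6% |
| 4 | 9.0% to 48% | 9.0% to 48.4% | 7.3% to 52.4% |
| 5 | 13.2% to 54.8% | 13.2% to 54.8% | 11.0% to 58.7% |

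The stated intervals reproduce, so the design precision is that of 16 subjects within one tumor type. SAP 5 and Protocol 14.1 attach these intervals to objective response; the protocol synopsis attaches them to DCR. The synopsis has a further line for 2/16 (3.4% to 36%) that does not reproduce (exact 2.3% to 34.4%). That is a separate matter and does not affect this point.

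**3. How many subjects per type are plausible.** SAP 5 gives final enrollment as 110. The rationale for Amendment 5 says that 55 patients had been treated when that amendment created EC3 and defined FEC. So about 110 − 55 = 55 remained, mostly for EC3, DEC2 and FEC together. A full FEC cohort would need 3 × 15 = 45, leaving about 55 − 45 = 10 for the others. The cap of 15 in all three types was therefore probably not reached. Counts by type are not given.

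**4. What a per-type row would show.** These counts are assumed, with an observed rate of 40% throughout, to show exact 95% intervals over a range of sizes:

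- 2/5: 5.3% to 85.3%
- 4/10: 12.2% to 73.8%
- 6/15: 16.3% to 67.7%

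**5. What pooling can hide.** Assumed counts again, at the FEC cap, which step 3 suggests is an upper bound: 3/15 (20%), 6/15 (40%) and 9/15 (60%) pool to 18/45 = 40%, with interval 25.7% to 55.7%. The pooled rate equals the middle type, and its interval excludes the observed rates of the other two. Other splits would give other patterns.

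**The case against.** Four arguments carry weight.

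- **The tables may exist.** A reader might infer that DCR outside sarcoma will only ever appear pooled. The documents do not support that. The table shells are a companion document that was not supplied, the SAP synopsis refers to unspecified subgroups of interest, and all collected data will be listed. FEC exploratory objective 6 in Table 2 mentions sarcoma only as an example. However, that objective is a comparison with monotherapy and names no other type, and the shells set layout whereas the SAP must specify the analysis. What stands is that the SAP text makes no commitment.
- **The pooled rate has a purpose.** A reader might infer that it answers none of the questions for which the cohorts were opened. Protocol 3.1 says otherwise: the phase 2 objective is the effect on DCR as monotherapy and in combination, which a rate by treatment addresses. Protocol 14.3.3 does not rank the overall rate below the tumor-type rates.
- **DCR's rank varies.** Table 2 makes it primary for DEC2 and FEC, but the SAP synopsis and Protocol 4.3 place it under secondary objectives. The planned tabulation is the same either way.
- **The numbers are small.** Step 3 supports this. It is a reason to show counts and wide intervals, or to declare a restriction, but the SAP does neither.

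A reader might also suspect selective reporting because only sarcoma is named. Nothing in the documents shows that.

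**Conclusion.** The discrepancy stands and should be corrected. The protocol plans DCR by tumor type in two places and the expansion groups were sized on that basis. The SAP commits to none of it, since even the sarcoma subgroup is optional, and its statement of no changes is inaccurate here.

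The types documented as affected are hepatocellular carcinoma and breast cancer in FEC. For DEC2 the same wording would omit any non-sarcoma expansion type, but those types are not in the supplied text; only the maximum of 44 subjects is.

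The effect is the omission of planned descriptive estimates. It does not bias the pooled rate as a summary of the subjects treated. The estimates would be imprecise: already 7.3% to 52.4% at 4/16, and wider at the smaller numbers that are likely. The conclusion rests on the SAP text without the table shells, and on no assumption about actual results.

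**What to change.** In SAP 7.5, replace the sarcoma-only line with each tumor type enrolled as an expansion group in DEC2 and FEC. In SAP 9, state that DCR with its exact 95% interval will be tabulated by treatment and tumor type alongside the pooled rate, which keeps its present standing. For types with very few subjects, give x/n only, with the threshold stated. If a restriction to sarcoma is intended, record it with its reason in SAP 13 in place of the present statement.

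The cost is a few table rows, using a variable that is already collected. The drawback is wide intervals, so the rows should be labelled descriptive and not used to rank tumor types.

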1. TOTAL TUMOR BURDEN (TTB)

Step 1: If all 3 dimensions are reported, volume = (longest*shortest*depth*0.63)

Step 2: If not all 3 dimensions are reported and longest diameter is reported, volume calculation is based on the longest diameter measurement.

1. If $. < \text{longest} < 1.5 \text{ cm}$, volume = 1 cm^3
2. If $1.5 \leq \text{longest} \leq 4 \text{ cm}$, volume = $\text{longest}^3/2$
3. If $4 < \text{longest} < 9 \text{ cm}$, volume = $\text{longest}^3/3$
4. If $\text{longest} \geq 9 \text{ cm}$, volume = $\text{longest}^3/4$
5. If shortest is only measurement reported, Diameter = shortest and follow step 2 tasks 1 to 4 for volume calculations

Step 3: Sum all calculated volume values across target and bystander tumors.

2. % DOSED TTB

Step 1. Calculate TTB of all of a patient's bystander and target tumors reported in the database using the TTB formulas above.

Step 2. Calculate patient's cumulative dose of INT230-6

Step 3. Calculate % Dosed TTB as (cumulative dose / Patient TTB) * 100.

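### SAP 7.5 and Appendix 1 give different lesion lists for total tumor burden; the 7.5 list includes post-baseline tumors, so some subjects could move from ≥40% to <40% dosed

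*SAP*

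**What the plan says.** SAP 7.5 lists a subgroup split by whether at least 40% of tumor burden was injected. For the denominator it states that "tumor burden is calculated based on EDC documentation of target, bystander, non-target, and new tumors". The next sentence describes the split as a share "of baseline total tumor burden injected overall (during the course of therapy) and at first dose will be explored". For the numerator it says "For overall, the sum of all injection volumes will be used in the calculation".

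SAP Appendix 1, item 1, gives volume formulas for each tumor and ends with "Sum all calculated volume values across target and bystander tumors". Item 2 repeats the two classes, referring to a patient's "bystander and target tumors reported in the database using the TTB formulas above", and then says "Calculate % Dosed TTB as (cumulative dose / Patient TTB) * 100". The worked example at the end of the appendix is presented as a baseline burden and contains two target and two bystander tumors.

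The SAP Synopsis refers to the burden the subject came in with and names no lesion classes. SAP 9.1 lists baseline TTB, percent dosed and the 40% category for each subject. SAP 9.2 plans Kaplan-Meier overall survival curves for monotherapy subjects below and at or above 40%, and for monotherapy sarcoma subjects at or above 40%. These are drawn in three analysis populations, and hazard ratios are optional.

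**The concern.** One grouping variable has two denominators. A programmer who follows 7.5 and one who follows Appendix 1 would each be complying with the SAP, yet could place the same subject in different groups.

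The new-tumor class is the more serious part. A lesion that first appears on treatment cannot be part of a baseline burden, so 7.5 conflicts with its own next sentence and with the Synopsis as well as with Appendix 1. If 7.5 is coded as written, something that happens after the first dose helps decide which survival curve a subject joins, although survival is counted from the first dose.

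The 40% split also bears on the SAP's research hypothesis, which links treating enough of the visible disease to longer survival. The lesion list should therefore be settled before anyone sees the curves.

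**Working it through.** **Inputs.** Volume with three dimensions is longest × shortest × depth × 0.63 (Appendix 1, item 1). Volume from the longest diameter L alone is 1 cc below 1.5 cm, L³/2 from 1.5 to 4 cm, and L³/3 above 4 and below 9 cm (same item). Percent dosed is cumulative dose / TTB × 100 (item 2). The cut is 40% (SAP 7.5).

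**1. Reproduce the SAP's example.**
- 4 × 3 × 3 × 0.63 = 22.68
- 2 × 1 × 1.5 × 0.63 = 1.89
- 2 × 1 × 1 × 0.63 = 1.26
- 1.5 × 1.2 × 1 × 0.63 = 1.134
- TTB = 26.964 cc, as printed

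The displayed formula uses 20 + 2 = 22 mL: 22 / 26.964 = 81.59%, against about 81.5% printed. The text beside it narrates 20 + 1 = 21 mL, which gives 77.88%. Both doses are carried below.

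**2. Direction.** Let T be the Appendix 1 burden, D the dose and V the volume of any non-target and new lesions. Appendix 1 gives D/T and 7.5 gives D/(T + V). Since V ≥ 0 and D is the same, the 7.5 percentage is never higher. Subjects can move only from ≥40% to <40%, and not at all if V = 0.

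**3. Where the example subject crosses.** The condition D/(T + V) < 0.40 means V > D/0.40 − T.
- 22 mL: 55.0 − 26.964 = 28.04 cc. As one lesion, L = (2 × 28.036)^(1/3) = 3.83 cm.
- 21 mL: 52.5 − 26.964 = 25.54 cc, or L = (2 × 25.536)^(1/3) = 3.71 cm.

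The 22 mL threshold does not survive rounding down. A 3.8 cm lesion adds 3.8³/2 = 27.44 cc, and 22 / 54.40 = 40.44%, still above the cut.

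**4. General rule.** For a subject at P% under Appendix 1, D/0.40 = (P/40) × T, so the subject crosses when V > (P/40 − 1) × T.

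| P under Appendix 1 | Added volume needed, as share of TTB |
|---|---|
| 41% | 2.5% |
| 45% | 12.5% |
| 50% | 25% |
| 60% | 50% |
| 80% | 100% |

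**5. Illustration.** The added lesion sizes and the 12 mL dose are assumptions; the tumors are those of the SAP's example.

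| One added lesion | Volume (cc) | 22 mL | 21 mL | 12 mL |
|---|---|---|---|---|
| none | 0 | 81.6% | 77.9% | 44.5% |
| 1.2 cm | 1 | 78.7% | 75.1% | 42.9% |
| 2 cm | 4 | 71.1% | 67.8% | 38.8% |
| 3 cm | 13.5 | 54.4% | 51.9% | 29.7% |
| 4 cm | 32 | 37.3% | 35.6% | 20.4% |
| 5 cm | 41.7 | 32.1% | 30.6% | 17.5% |

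Far above the cut it takes a large lesion to change the group; near the cut a 2 cm lesion is enough.

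**The case against.** The best defence is that Appendix 1 is the working rule and 7.5 is loose wording. Only the appendix gives an algorithm and an example, SAP 7.1 sends the reader there for programming notes, and the baseline language in 7.5, 9.1 and the Synopsis suggests that new tumors were never meant to count. This is probably the intent, and it points to the simplest fix. It does not remove the conflict. The appendix says it supplies definitions missing from the main text, whereas this one is in the main text with different content. No sentence gives the appendix precedence.

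A second defence is that the extra lesions would seldom carry a volume. SAP 9 classes non-target lesions as non-measurable, and the 9.1 listing specifies volume only for target and bystander tumors. That limits the reach. But protocol 18.1.5 asks for actual measurements of baseline non-target lesions, protocol 18.1.3 has new lesions measured, and the appendix can turn a single diameter into a volume.

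A third is that the stakes are modest: the subgroup is optional, overall survival is exploratory, and neither the primary safety endpoint nor the overall disease control rate uses the cut. This stands. The survival curves split at 40% are nevertheless planned outputs.

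A reader might go further and infer that 7.5 biases the survival comparison in favour of the ≥40% group, because subjects with new lesions drift below the cut. The documents do not show this. Subjects followed longer also have more scans on which a new tumor can be recorded, so the net direction is open. Nor do they show that subjects can switch either way, or that many would.

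**Conclusion.** The inconsistency is real and should be resolved. The SAP gives two lesion lists for one denominator, and the longer list includes post-baseline tumors that contradict the stated baseline definition. Any reclassification runs from ≥40% under Appendix 1 to <40% under 7.5. It needs added volume above (P/40 − 1) × TTB, which for the SAP's own example is 28.04 cc at 22 mL or 25.54 cc at 21 mL.

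This rests on the numerator being the same under both rules and on the extra lesions having a recorded diameter. The documents contain no lesion-level data, so neither the number of subjects affected nor the size or direction of any effect on the curves can be stated. The finding concerns an exploratory exposure split and does not touch the primary endpoint.

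**What to change.** Before database lock, adopt one baseline-only definition of TTB and use it in SAP 7.5, 9.1, 9.2 and Appendix 1. The simplest change is to delete the non-target and new classes from 7.5 so that it matches Appendix 1. New tumors should never enter the denominator. Items 1 and 2 of Appendix 1 should also state the baseline time point, which at present only the worked example does.

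Protocol 5.2.1 allows new lesions to be injected during maintenance and 7.5 sums all injections, so one sentence should say whether that dose counts in the numerator. The 21 versus 22 mL slip in the example can be corrected in the same edit.

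A sensitivity analysis that adds baseline non-target lesions with a recorded diameter is optional. The core change costs a few words. The sensitivity analysis would mean repeating whichever 40% curves are chosen, which are planned in three populations and also in sarcoma.
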